8.1.6 Causality

The investigator's assessment of causality must be provided for all AEs (serious and non-serious). An investigator's causality assessment is the determination of whether there exists a reasonable possibility that the investigational product caused or contributed to the AE. In addition, if the investigator determines a SAE is associated with study procedures, the investigator must record this causal relationship in the source documents and on the SAE form and report such an assessment in accordance with the SAE reporting requirements. The investigator will use medical consideration and use the following categories of causality to determine the relatedness of an AE with the study drug based on the following definitions. Not all criteria in each category of relatedness must be present.

- Definitely Not Related (not drug related): The subject did not receive study drug, OR the temporal sequence of the AE onset relative to the administration of the study drug is not reasonable, OR there is another obvious cause of the AE
- Probably Not Related (not drug related): there is evidence of exposure to study drug, there is another more likely cause of the AE, dechallenge (if performed) is negative or ambiguous, rechallenge (if performed) is negative or ambiguous

- Possibly Related (drug related): there is evidence of exposure to study drug, the temporal sequence of the AE onset relative to administration of the study drug is reasonable, the AE could have been due to another equally likely cause, dechallenge (if performed) is positive
- Probably Related (drug related): there is evidence of exposure to study drug, the temporal sequence of the AE onset relative to administration of the study drug is reasonable, the AE is more likely explained by the study drug than by another cause
- Definitely Related (drug related): there is evidence of exposure to study drug, the temporal sequence of the AE onset relative to administration of the study drug is reasonable, dechallenge is positive, rechallenge (if feasible) is positive, the AE shows a pattern consistent with previous knowledge of the test drug or a test drug class

8.1.7 Expectedness

The expectedness of an AE is assessed by the Investigator in the overall classification of AEs and SAEs for regulatory reportability.

8.2 Serious Adverse Events

The definitions and reporting requirements of FDA and ICH Guidelines for Clinical Safety Data Management, Definitions and Standards for Expedited Reporting, Topic E2A, will be adhered to.

8.2.1 Serious Adverse Event Definition

An AE is considered an SAE if at least one of the following conditions applies:

- Death: An AE that results in death is any subject death within 30 days of the last dose of study drug administration. The cause of death or AE that resulted in a fatal outcome is the SAE
- Life-threatening AE: An AE that places the subject, in the view of the investigator or the sponsor, at immediate risk of death from the event as it occurred (i.e., this does not include an event that had it occurred in a more severe form might have caused death)
- Results in a persistent or significant incapacity or substantial disruption of the ability to conduct normal life functions: Any substantial disruption of a person's ability to conduct normal life functions
- Inpatient hospitalization or prolongation of existing hospitalization: Hospitalization refers to admission of a subject into a hospital for any length of time
- A congenital anomaly/birth defect: A fixed, permanent impairment established at or before birth
- Cancer: Occurrence or diagnosis of a new cancer during the study is considered an SAE. A new cancer is a cancer that is histopathologically different than the cancer under study in the trial (i.e., does not include metastatic or progressive disease)
- Overdose: Occurrences of overdose must be reported as an SAE
- Important medical event: Medical and scientific judgment should be exercised in determining whether an event is an important medical event. An important medical event may not result in death, be life-threatening, or require hospitalization. However, if it is determined that the event may jeopardize the subject and/or may require intervention to prevent one of the other outcomes listed in the definition above, the important medical events should be reported as serious. Examples of such events are intensive treatment in an emergency room or at home for allergic

bronchospasm, blood dyscrasias, or convulsions that do not result in hospitalization; or the development of drug dependency or drug abuse.

AEs (reported from clinical studies) that require hospitalization or prolongation of hospitalization are considered serious. Any initial admission (even if less than 24 hours) to a health care facility meets these criteria. AEs that require emergency room care that do not result in hospital admission are not SAEs unless assessed by the investigator to be an important medical event. Hospitalization does not include the following: Hospice facilities, Respite care, skilled nursing facilities, Nursing home, Routine emergency room admissions, and same day surgeries (as outpatient/same day/ambulatory procedure)

Hospitalization or prolongation of hospitalization in the absence of a precipitating AE is not in itself an SAE. Examples include: social admission (e.g., subject has no place to sleep), optional admission not associated with a precipitating AE (e.g., for elective cosmetic surgery that was planned prior to study enrollment [appropriate documentation is required for these cases]), hospitalization or prolongation of hospitalization for scheduled therapy of the target malignancy of the study is not considered an SAE

8.2.2 Reporting Adverse Events

Written Investigational New Drug (IND) safety reports will be submitted to the FDA by the IND sponsor, for serious, unexpected suspected adverse reactions within 15 calendar days of the sponsor determining that the information requires reporting. If the event is fatal or is deemed to be life threatening, the report will be made within 7 calendar days. The IND sponsor will also make an assessment of whether the event constitutes an unanticipated problem posing risks to subjects or others (UP). This assessment will be provided to the Emory University IRB, which, in turn will make a final determination. If the Emory IRB determines an event is a UP it will notify the appropriate regulatory agencies and institutional officials. The Sponsor- Investigator is responsible for reviewing all IND Action Letters, Safety Reports and any other safety related Investigator Notification and determining the action to be taken (i.e. prompt reporting to the IRB, consent change/modification, routine reporting, etc).

The following information about the subject and the event will need to be collected and available:

- Investigator identification
- Subject identification code (e.g., sex, age, or date of birth)
- Information on study drug (e.g., start/stop date, dose and frequency of study drug administered)
- Description of event

In addition to the above information, the sponsor will require the investigator's assessment of the following:

- Severity of the SAE
- Relationship of the SAE to the study drug
- Outcome of the SAE

8.2.3 Follow-up Information of Serious Adverse Events

Appropriate diagnostic tests should be performed and therapeutic measures, as medically indicated, should be instituted. Appropriate consultation and follow-up evaluations should be carried out until the

event has resolved or is otherwise explained by the investigator. For all SAEs, the investigator is obligated to pursue and provide information to the appropriate regulatory agencies. There should be routine follow-up through and including 30 days after the last administration of assigned study treatment or the investigator/ subject decision to discontinue treatment, whichever occurs later, in all subjects in order to monitor for the occurrence of SAEs. If an SAE continues after the 30-day evaluation period, then the subject must be followed until the event resolves or returns to baseline. The medical monitor may specify a longer period of time if required to assure the safety of the subject.

8.3 *Other Safety Issues*

8.3.1 Pregnancy

Females of childbearing potential and fertile males will be informed as to the potential risk of conception while participating in this study and will be advised that they must use effective contraception from beginning study drug through at least 30 days after the end of treatment. A pregnancy test will be performed on each pre-menopausal female of childbearing potential immediately prior to beginning study drug. A negative pregnancy test must be documented prior to administration of study drug. If a subject is confirmed pregnant during the trial, study drug administration must be discontinued immediately. The investigator must immediately notify the appropriate regulatory agencies of this event and record the pregnancy on a Pregnancy Form. The investigator must also report follow-up information to the appropriate regulatory agencies regarding the course of the pregnancy, including perinatal and neonatal outcome, regardless of whether the subject has discontinued participation in the study. If the pregnancy results in the birth of a child, additional follow-up information may be requested. If the pregnancy results in spontaneous abortion or stillbirth, the event should be reported as an SAE. Pregnancy outcomes must be collected for the female partners of any males who took study drug in this study. Consent to report information regarding these pregnancy outcomes should be obtained from the female partner.

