5.1 Schedule of Events

The following describes the procedures/tests required for this study:

Screening, on study, and end of study procedures are shown in **Table 3**. Screening tests and procedures to establish eligibility of the subject for the trial will be done within 14 days prior to initiation of study drug. Evaluation, visit samples or activities should occur within range defined below.

Table 3. Schedule of Events

	Screening ± 14days	Day1	On PIO and TKI		Off PIO and TKI		End of Treatment	12 Long-Term Follow up
			Evaluations on day 14 ± 2days	Evaluations on days 28 ± 2days then monthly ± 2days	Monthly Evaluations ± 2days for first 3 months	Quarterly Evaluations ± 7days for one year		
¹ Informed Consent and Registration	X							
² History and Demographics	X							
³ CML history, prior therapy, and response	X							
⁴ Vital Signs, Physical Examination	X		X	X			X	
⁵ Concomitant medications	X		X	X			X	
⁶ CBC and differential, and Serum Chemistries	X		X	X			X	
⁷ Urine HCG	X							
⁸ Blood qRT-PCR for BCR-ABL1	X			X	X	X	X	X
⁹ Diary card			X	X				
¹⁰ MMAS-8			X	X				
¹¹ Adverse Events Assessments		X						→
PIO administration		X		X				

¹**Informed Consent:** All subjects must take part in the informed consent process prior to any study related activity. During the consent process, the person obtaining consent must inform the subject of all elements of informed consent. Adequate time must be allowed for questions and for the subject to make a voluntary decision. No protocol-specific procedures are to be performed until the subject has signed and dated the

IRB approved informed consent form. Each subject's participation in the trial begins with the signing and dating of the informed consent form.

²*Medical/Surgical History and Demographics:* Medical/surgical history that includes diagnoses and therapies as well as demographic information that consists of the subject's age, gender, race, and ethnicity will be recorded.

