End of Treatment or Early Termination Procedures: The End-of-Treatment (or early termination) Visit should be performed within 2 weeks (14 days) of the subject's last dose of study drug or the subject/investigator decision to end treatment, whichever is later. Subjects will also return to the clinic or

will be contacted for a safety follow-up assessment 30 days \pm 3 days after the last dose of study drug was taken.

¹²*Long Term Follow-up:*

- **Safety:** All AEs ongoing or starting within 30 days after the End-of-Treatment must be recorded on the case report form (CRF). After this time, ongoing AEs thought to be at least possibly study-drug related and all ongoing serious adverse events (SAE) should be followed at least every 4 weeks until they resolve to baseline (or CTCAE grade ≤ 1), stabilize, or are considered to be chronic or irreversible.
- **Relapse-free Survival:** After 2 years of follow-up off TKI, if MMR is lost at any time, or if subjects withdraw from study for toxicity or any reasons, information on disease status (qRT-PCRs) will be collected once a year for 5 years as part of the Long-Term Follow-up. This information does not need to be obtained during a visit; review of local hematologist's records is acceptable.

5.2 **Description of Study Visits**

5.2.1 **Visit 1 (Day -14 to -1): Screening**

- Obtain written informed consent
- Record demographic data including age, gender, and race
- Review medical, surgical, and CML history described above.
- Record prior and concomitant medications including start/stop dates, indication, dose and frequency taken within 30 days of Day 1.
- Collect blood samples for CBC with differential count and serum chemistries.
-
- Collect urine for pregnancy test for female subjects who are not postmenopausal or surgically sterile. If positive, repeat and confirm results within a week and prior to start of study drug. A second positive test will result in exclusion of the subject from the study.
- Unless done within 72 hours, measure and record height in cm and weight in kg, record vital signs. Measure body temperature, systolic / diastolic blood pressure (BP) and pulse rate. Perform and record physical examination.
- Collect blood samples for qRT-PCR of *BCR/ABL1* unless done it within 30 days

5.2.2 **Visit 2 (Day 1): Baseline/Drug Dispensing/Initiation of Treatment**

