- Review and document all inclusion and exclusion criteria to ensure that subjects meet all inclusion criteria and none of the exclusion criteria.
- Record AEs as part of standard of care.
- Dispense PIO at 30 mg/d and instruct subjects how to take study drug, daily every 24 hours and how to fill the diary card.

5.2.3 **Visits 3 (Days 14 \pm 2): Early Follow-up**

- Measure and record height in cm and weight in kg. Record vital signs. Measure body temperature, systolic/diastolic BP and pulse rate. Perform and record physical examination.

- Record medications including start/stop dates, indication, dose and frequency for any changes since previous visit.
- Collect blood samples for CBC with differential count and serum chemistries.
- Assess study drug compliance by pill count, review of the diary card and MMAS-8.
- Assess and record AEs and SAEs

5.2.4 Visits 4+ (Day 28 ±2, then q28+/-2 days during combination of PIO and TKI)

- On day 28, measure and record height in cm and weight in kg. Record vital signs. Measure body temperature, systolic / diastolic BP and pulse rate. Perform and record physical examination. Unless new symptoms occur, these will be performed every other month as part of standard of care.
- On day 28, record medications including start/stop dates, indication, dose and frequency for any changes since previous visit. Unless new symptoms occur, these will be performed every other month as part of standard of care.
- On day 28, collect blood samples for CBC with differential count and serum chemistries. Unless new symptoms occur, these will be performed every other month as part of standard of care.
- On day 56, in the absence of grade 2 or higher toxicities, PIO doses will be increased to 45 mg/d
- Dispense drug supply for self-dosing, remind subjects of dosing instructions, and obtain all unused study drug
- Assess study drug compliance by pill count, review of the diary card and MMAS-8.
- Collect blood samples for qRT-PCR of *BCR/ABL1* every month.
- Assess and record AEs and SAEs continuously

5.2.5 Post-discontinuation of PIO and TKI Visits (Monthly for 3 months ± 2 days and quarterly ±7 days for 1 year and biannually thereafter)

- Collect blood samples for qRT-PCR of *BCR/ABL1* as part of standard of care
- Assess and record AEs and SAEs continuously

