7.2 Allocation of Treatment

The results of screening assessments for each subject will be reviewed by the study principal investigator (PI), who will approve each subject. Upon this approval, subjects will receive a 28 days (1 cycle) + 2 days supply of 30 tablets of PIO.

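### Section 8.3.1 requires a pregnancy test directly before the first pioglitazone dose, but the visit schedule has only a screening test, which may be up to 14 days old at dosing

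*Combined protocol and SAP*

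**What the plan says.** Section 8.3.1 (Pregnancy) sets the timing of the test: "A pregnancy test will be performed on each pre-menopausal female of childbearing potential immediately prior to beginning study drug". It then adds a documentation rule: "A negative pregnancy test must be documented prior to administration of study drug". It gives no number of hours or days for the first statement and no maximum age for the result in the second.

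The operational sections read differently:

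- Section 5.1: "Screening tests and procedures to establish eligibility of the subject for the trial will be done within 14 days prior to initiation of study drug".
- Table 3: the urine HCG row has a single mark, in the Screening column. Day 1 and all later columns are empty. Footnote 7 restricts who is tested and says nothing about when.
- Section 5.2.1 (Visit 1, Day -14 to -1): "Collect urine for pregnancy test for female subjects who are not postmenopausal or surgically sterile". A second test is conditional: "If positive, repeat and confirm results within a week and prior to start of study drug".
- Section 5.2.2 (Visit 2, Day 1): a review of eligibility, recording of adverse events, and dispensing of pioglitazone 30 mg/d with instructions. No pregnancy test is listed.
- Section 4.1, inclusion criterion 7: women of childbearing potential need a negative urine test at enrolment.

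**The concern.** The rule on timing sits in a late safety section, while Table 3 and Section 5.2 are what staff work from visit by visit. Staff who follow those lists exactly can breach Section 8.3.1 without noticing.

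What is at stake is fetal exposure. Pregnancy is listed as a contraindication to pioglitazone in Section 1.5.4 and is exclusion criterion 13. The contraception provisions do not protect the interval between test and first dose: Section 8.3.1 starts the requirement when study drug starts, and inclusion criterion 7 covers the treatment period and the 3 months after it. Table 3 schedules no later pregnancy test either, so the screening test is the only planned check.

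Two features of this trial add weight. Section 1.6 cites the bar on conception during TKI treatment as one reason for interest in stopping TKIs. Section 3.1 lets subjects enter before they have restarted their TKI. Some women may therefore be off TKI during screening and about to start both drugs.

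**Working it through.** There is no statistical figure to reproduce. The check compares the sections and counts days.

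**1. Age of the scheduled test at first dose.** Inputs: Visit 1 runs from Day -14 to Day -1 (Section 5.2.1), and pioglitazone is dispensed and started on Day 1 (Section 5.2.2). The numbering has no Day 0, so the gap from Day -d to Day 1 is 1 - (-d) - 1 = d days.

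- Test on Day -14: 1 + 14 - 1 = 14 days before the first dose.
- Test on Day -1: 1 + 1 - 1 = 1 day before the first dose.

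The range is 1 to 14 days. The upper end agrees with the 14-day limit in Section 5.1.

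**2. Tests scheduled on Day 1.** Table 3: 0. Section 5.2.2: 0.

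**3. Does any scheduled step renew an early negative result?**

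| Provision | What it requires | Is a negative from Day -14 renewed? |
|---|---|---|
| Conditional repeat, Section 5.2.1 | Second test after a positive | No; it does not apply to a negative |
| Day 1 eligibility review, Section 5.2.2: "Review and document all inclusion and exclusion criteria to ensure that subjects meet all inclusion criteria and none of the exclusion criteria" | Checking and documenting criteria | No; it can be met from the screening record |
| Approval, Section 7.2: "The results of screening assessments for each subject will be reviewed by the study principal investigator" | Review of existing screening results | No |
| Documentation rule, Section 8.3.1 | A negative on file before dosing | No; no maximum age is given |
| Inclusion criterion 7 | Negative urine test at enrolment | Not necessarily; see step 4 |

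**4. Inclusion criterion 7.** This is a third wording of the timing. Section 5.3 allows enrolment once screening procedures are complete and all criteria are met. The protocol fixes no interval between enrolment and Day 1. The criterion may shorten the gap in practice, but it does not tie the test to the day of dosing.

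**5. Can a site comply with everything?** Yes. A test on Day -1 arguably satisfies both Section 8.3.1 and the schedule. A test early in the window satisfies the schedule but not Section 8.3.1.

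**The case against.** The strongest reply is that nothing is contradictory. Section 8.3.1 is current, mandatory text, and neither Table 3 nor Section 5.2 forbids a further test or says that the screening test replaces it. On that reading, a site that doses on a Day -14 negative has simply broken the protocol, and the fault is an omission from the visit lists. This is fair as a description: the protocol taken as a whole does call for a test close to dosing. It does not remove the problem, because the visit lists are where procedures get done, and they omit this one.

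A second reply is that inclusion criterion 7 already asks for a negative test at enrolment, and that the Day 1 review must confirm it. This narrows the likely gap, so the 14-day figure is the outer limit of Sections 5.1 and 5.2.1 taken together. It does not close the gap, since enrolment is not tied to Day 1.

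A third reply is that the harm is not quantified. That stands. The protocol does not say how many of the 26 subjects will be women of childbearing potential, and nothing in it supports an estimate of pregnancies missed. Exclusion criterion 13 and the rule to stop study drug at once on confirmed pregnancy also remain in force.

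Finally, a Day 1 test is not the only possible remedy; stating a window for the Section 8.3.1 test would also work. That is true, but the window would still have to be carried into Table 3 and Section 5.2 to have any effect.

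**Conclusion.** The point holds. Section 8.3.1 and the visit schedule do not agree on when the pregnancy test is done, and the schedule permits a first dose on a negative result 1 to 14 days old, with no test listed on Day 1. The conclusion rests on two readings: that the day numbering has no Day 0, and that the requirement in Section 8.3.1, which carries no figure, means something closer to dosing than the full screening window.

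The number of women affected is unknown and can be no more than the 26 subjects in the trial. The matter is one of subject safety and has no bearing on the efficacy endpoints, the two-stage design or any analysis. It should be corrected, but it does not threaten the trial's conclusions.

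**What to change.** - In Table 3, mark urine HCG in the Day 1 column for women of childbearing potential.
- In Section 5.2.2, add a urine pregnancy test ahead of the dispensing item, with a negative result documented before any pioglitazone is handed out.
- Leave the screening test in Section 5.2.1 as it is; it still serves to identify ineligible subjects early.

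The cost is one mark in a table, one line of text, and at most one extra urine test per eligible woman at an existing visit. Nothing is added beyond what Section 8.3.1 already asks for.
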